FULL PROTOCOL TITLE:
**EXPERIENCING LOSS AND PLANNING AHEAD STUDY: CARING FOR A RELATIVE OR FRIEND
WITH DEMENTIA**

ACRONYM: ELPAS

Chief Investigator:

[name], BA(Hons) PhD, Senior Research Fellow, Marie Curie Palliative Care
Research Department, Division of Psychiatry, UCL

Supported by:

Alzheimer's Society Senior Fellowship award 325 (AS-16-004)

Sponsored by:

University College London (UCL)

Protocol version number and date:

Version 1: 2 October 2017

R&D / Sponsor Reference Number(s):

17/0477

NCT number:

NCT03332979

Study Registration Number:

PROTOCOL VERSIONS

Version Stage	Versions No	Version Date	Protocol updated & finalised by;	Appendix No detail the reason(s) for the protocol update
Current	1	2 October 2017	[name] (Chief Investigator)	NA

DECLARATIONS

The undersigned confirm that the following protocol has been agreed and accepted and that the investigator agrees to conduct the study in compliance with the approved protocol and will adhere to the Research Governance Framework 2005 (as amended thereafter), the Trust Data & Information policy, Sponsor and other relevant SOPs and applicable Trust policies and legal frameworks.

I (investigator) agree to ensure that the confidential information contained in this document will not be used for any other purposes other than the evaluation or conduct of the clinical investigation without the prior written consent of the Sponsor.

I (investigator) also confirm that an honest accurate and transparent account of the study will be given; and that any deviations from the study as planned in this protocol will be explained and reported accordingly.

Chief Investigator:

Signature:..... **Date:**.....

Print Name(in full): [name]

Position: Senior Research Fellow

On behalf of the Study Sponsor:

Signature:..... **Date**...../...../.....

Print Name(in full):.....

Position:.....

STUDY SUMMARY

Identifiers	
IRAS Number	232091
REC Reference No	
Sponsor Reference No	17/0477
Other research reference number(s) (if applicable)	
Full (Scientific) title	Experiencing Loss and Planning Ahead Study (ELPAS): Caring for a relative or friend with dementia.
Health condition(s) or problem(s) studied	Pre-death grief experience by family and friend carers of people with dementia
Study Type i.e. Cohort etc	Cross-sectional cohort study
Target sample size	150
STUDY TIMELINES	
Study Duration/length	2.5 years
Expected Start Date	2/10/2017

1 INTRODUCTION

The course of dementia over many years, gradual losses and uncertain life expectancy can mean that family carers experience feelings and symptoms of grief before the death of the person for whom they are caring. UK guidelines recommending that carers are offered information about bereavement supports and dementia progression are rarely followed in practice.

This study aims to examine the relationship between carers' feelings of grief before the death of a person with dementia and how well they are prepared for that death. The study involves completing a questionnaire schedule with 150 carers of people with dementia (across all stages of dementia and for people with dementia living at home or in a care home). Twenty of these carers will be purposively selected to complete an additional semi-structured interview to further explore the research questions. The questionnaires will examine whether being prepared for end of life is linked to having lower levels of grief. Preparation will be measured by important factors shown in research including: knowledge of dementia progression; knowledge of the person with dementia's end of life preferences; communication with healthcare professionals; family support; and having a Power of Attorney or advance directive in place. The study is one component of a larger senior fellowship being undertaken by the CI and will inform subsequent development of a resource for supporting carers to help prepare for end of life care and manage grief. The study was informed by the Alzheimer's Society Research Network who will also be involved throughout the study. It will increase understandings of how we can better support grieving carers and help them plan and prepare for end of life care. This is a critical area given that dementia is now the leading cause of death in the UK [1] and family and friend carers are relied on to meet an ever increasing proportion of the support and care needs for their relatives living with dementia in this time of austerity.

2 BACKGROUND AND RATIONALE

Grief is often felt before the death of a friend or relative with dementia. Grief before the death can be triggered by losses associated with dementia causing carers to experience sorrow, anger, yearning and acceptance that can wax and wane from diagnosis to the end of life [2]. It occurs due to the lengthy and uncertain disease trajectory; compromised communication between the person with dementia and family and friends; and changes in relationship quality and carer freedom.[2] Grief before the death can contribute to carer burden and depression.[2] Between 47-71% of family carers of people with dementia experience grief before the death and 20% experience complicated grief after the death.[3] Higher grief prior to death is associated with complicated grief after death [4], so emotional support during care rather than solely after the death may be beneficial.[5]

Preparation for end of life has medical, psychosocial, spiritual and practical components, [6, 7] including having a family member or healthcare professional to help make decisions, knowing what to expect about the terminal condition and having finances in place.[8] Good communication with healthcare providers to discuss prognosis, treatments, cultural, spiritual and practical issues; and dealing with family conflict is critical.[6] Preparation for end of life is associated with a lower likelihood of complicated grief in bereavement [9-11] but has not been explored in the context of grief before the death (Figure 1). Preparation for end of life is influenced by socioeconomic factors associated with health literacy (Figure 1). Low health literacy is more common amongst those from more deprived backgrounds, ethnic minorities, older people and those with chronic health conditions.[12] In the UK a third of older adults have difficulty interpreting basic health information.[13] Despite the potential benefits of end of life discussions with carers, there are many barriers to such discussions.[14, 15] Carers struggle to formalise in writing future wishes on behalf of the person with dementia and professionals tend to be reluctant to initiate end of life discussions.[16] Family conflict can deter end of life decision making.[17] Factors reflecting preparation for end of life are potentially modifiable suggesting that improving preparation could reduce grief before the death.

[figure not shown]

Figure 1: Existing evidence linking preparation for end of life and grief (before and after the death)

This will be the first UK study to assess the prevalence of grief before the death amongst a sample of carers for people with all stages of dementia and living either at home or in a care home. It will be one of few studies to explore whether modifiable factors showing preparation for end of life are associated with lower levels of grief before the death. The modifiable factors reflecting preparation for end of life include:

- carers' having a good knowledge of dementia progression,
- high health literacy,
- a lasting (enduring) Power of Attorney,
- knowing the end of life wishes of the person with dementia and
- being satisfied with support from their social network.

Knowing which modifiable factors reflecting preparation for end of life are most closely associated with grief before the death will inform the development of a resource for carers. If this study is successful in developing the first evidence-based intervention for family carers to reduce grief before the death and improve preparation for end of life, it has the potential to reduce carer distress during the lifetime of the person with dementia, bringing benefits for the person with dementia as well as their carer. It will enable discussions to ensure care at the end of life is planned and in accordance with the person's wishes; and may reduce the prevalence of complicated grief after the death of the person with dementia.

The study builds on the previous research of the CI and the Marie Curie Palliative Care Research Department (MCPCRD), within UCL's Division of Psychiatry where the study will take place. In 2013, the MCPCRD systematically reviewed the prevalence and predictors of grief before and after the death in carers of people with dementia.[3] Our analysis of primary care data found that carers of people with dementia used more psychotropic drugs prior to bereavement than other carers.[18] Mentor [name] and supervisor [name] reviewed evidence on advance care planning (ACP) in dementia and found considerable barriers to implementing ACP in practice. They found that carers' capacity to make best interest decisions about end of life is influenced by religious beliefs, education, guilt and burden.[19] Their qualitative work identified that even in mild stages, people with dementia have difficulty envisaging themselves being more dependent on others.[14] The 3-year Compassion study, led by [name] and [name] (National Institute for Health Research [NIHR] portfolio ref. CRN-PCRN 12621; 12623) [20], involved a small cohort study of people with advanced dementia and their family carers. We found that 26% of carers reported depression, 41% anxiety and grief before death was high. Carers were offered minimal emotional support before and after their relative's death [21]. We developed the Compassion Intervention to promote integrated palliative

dementia care.[22, 23] This was tested in two care homes where the CI was employed as an Interdisciplinary Care Leader. Few carers were aware of common end of life symptoms.[24] The importance of studying grief and end of life support for carers of people with dementia was strongly endorsed by carers of the Alzheimer's Society Research Network whom the CI consulted in a specially convened focus group. Network members expressed major concerns in the current provision of end of life preparation and information as well as grief support, reinforcing this as a neglected topic requiring more research and development.

3 OBJECTIVES

3.1 Primary Objective

This study aims to examine the relationship between family and friend carers' feelings of grief before the death of a person with dementia and how well carers are prepared for that death.

The hypothesis that will be tested is that modifiable factors indicating preparation for end of life are associated with lower grief before the death in carers of people with dementia.

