3.2 Secondary Objectives

- To examine the prevalence and severity of grief before the death in carers of people with dementia (Quantitative interviews)
- To identify which modifiable factors reflecting preparation for end of life are most strongly related to grief before the death (Quantitative interviews)
- To examine the extent to which carers feel prepared for the future and end-of-life care for their relative with dementia (Quantitative and qualitative interviews)
- To explore whether carers recognize grief during caring and what supports they think would be helpful (Quantitative and qualitative interviews)
- To identify unmet needs for information about end of life symptoms and emotional support for carers (Qualitative interviews)
- To explore how carers experience and cope with changes in grief over time (Qualitative interviews)

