4.1 Quantitative interviews (n=150)

The study will aim to recruit 150 carers over a 15 month period starting in late 2017. The recruitment and consent process is described in detail in Section 6 and the power calculation in Section 7. Carers will provide written, informed consent before completing a face-to-face interview in a location of their choice. Previous experience in research with carers indicates that the majority will wish to be interviewed in their own home or the home of the person with dementia. Researchers will undertake the interview in pairs to begin with but on their own after training is complete. They will adhere to the UCL lone worker policy.

Researchers will ask questions and record answers on the Case Report Form (Appendix 1). The CRF contains demographic questions about the carer and some basic information about the person with dementia (such as dementia severity, type of diagnosis and time since diagnosis).

The Marwit-Meuser Caregiver Grief Inventory Short Form (MMCGI-SF) [25] will be used to assess severity of grief before death. This scale contains three subscales: heartfelt sadness and longing, worry and felt isolation, and personal sacrifice burden; a cutoff of 70/90 is considered a high level of grief.[25] The Clinical Dementia Rating scale will assess dementia severity based on the carer's report [26]. To test the primary hypothesis we will collect a number of measures to reflect the five modifiable factors that suggest preparation for end of life:

1. Greater knowledge of how dementia progresses (Dementia Knowledge Assessment Scale [27])
2. Greater knowledge of the person with dementia's end of life preferences (Discussed wishes regarding end of life with your relative? Have a good understanding of their wishes for end of life care?)
3. Having a lasting Power of Attorney or other formal advance directives in place - a proxy indication of "preparedness" (binary variable; any form of directive in place/not in place)
4. Higher satisfaction with communication with healthcare providers (Health Literacy Questionnaire [HLQ, excluding Social Support subscale] which examines how well carers understand health information and navigate the health system [28]) (See Appendix 2)
5. Higher satisfaction with support for health from social network (HLQ-Social Support subscale.[28])

A number of other measures have been included for other exploratory analysis and to control for possible confounders. These include:

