7 DATA ANALYSIS

7.1 Statistical Analysis

The statistical analysis will be overseen by the project statistician ([name]). Multivariable regression analysis will be used to enable us to explore the impact of a range of modifiable factors reflecting preparation for end of life on the MMCGI-SF, our main outcome. This type of analysis also allows us to control for potential confounding variables. The analysis will use the MMCGI-SF as the dependent variable with five predictor variables: knowledge of how dementia progresses; knowledge of the person with dementia's end of life preferences; having a lasting Power of Attorney or other formal advance directive in place; satisfaction with communication with healthcare providers; and satisfaction with support for health from your social network (detailed in Section 4.1).

The latter two items are extracted from the Health Literacy Questionnaire [28]. Health literacy is likely to be related to deprivation, which we will measure using the Townsend Deprivation Index. We will first examine whether there is collinearity between the health literacy and deprivation variables. If they are not related we will add deprivation as a covariate. Other potential confounding variables will be included in the analysis:

- Relationship type: being a spouse/partner, a child or another relationship (categorical variable; i.e. 2 covariates)
- Gender (binary measure)
- Care home status: living at home or in a care home (binary measure)
- Religiosity (continuous measure)

In total there are 10 potential covariates to be included in the model. A sample of 15 participants per covariate is preferable while ten may be sufficient.[34]. We will aim to recruit 150 participants for an adequately powered analysis.

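### Does the lack of an alpha and a decision rule for the five preparation factors leave the primary hypothesis without a usable analysis?

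*Combined protocol and SAP*

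**What the plan says.** Section 3.1 states the primary hypothesis: "The hypothesis that will be tested is that modifiable factors indicating preparation for end of life are associated with lower grief before the death". Section 4.1 gives the number of factors and repeats the intention: "To test the primary hypothesis we will collect a number of measures to reflect the five modifiable factors that suggest preparation for end of life". Each of the five is worded there so that more of it means better preparation, which makes the expected direction clear.

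Section 7.1 is the only statistical analysis text. It opens "Multivariable regression analysis will be used to enable us to explore the impact of a range of modifiable factors", then names the MMCGI-SF as dependent variable, the five predictors, and the confounders: relationship type, gender, care home status, religiosity and, conditionally, deprivation. It gives no significance level, sidedness, joint test, multiplicity approach or rule for declaring the hypothesis supported.

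Section 4.1 refers the reader to "the power calculation in Section 7". What Section 7.1 holds is a ratio: "A sample of 15 participants per covariate is preferable while ten may be sufficient".

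A separate secondary objective in Section 3.2 uses the same coefficients: "To identify which modifiable factors reflecting preparation for end of life are most strongly related to grief before the death".

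**The concern.** Sections 3.1 and 4.1 speak of a test, while Section 7.1 and Section 2 ("one of few studies to explore whether modifiable factors showing preparation for end of life are associated with lower levels of grief") speak of exploring. If the primary analysis is a test, five coefficients do not give one answer even at an agreed 5%. The plural in the hypothesis could mean the set taken together, any one factor, or every factor. The sample-size text cannot settle this, because a participants-per-covariate ratio implies no particular test or alpha.

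Two analysts could therefore fit the same model to the same data and differ on whether the hypothesis was supported. The rule could also be picked once the results are known, so readers might not be able to tell a pre-set test from an exploratory estimate.

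**Working it through.** **1. The plan's own figure.** Section 7.1 counts 10 covariates: 5 factors + 2 relationship terms + gender + care home + religiosity = 10. At 15 per covariate, 15 × 10 = 150, which reproduces the target. No alpha, effect size or power enters.

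**2. What is fixed and what is open.** Fixed: outcome, five predictors, confounders, direction. Open: the step from five adjusted coefficients to a verdict.

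**3. Three defensible rules.** Each allows support only toward lower grief.
- *Holm:* at least one factor significant after adjustment. With no true association this is in effect p < 0.05/5 = 0.01 with a negative sign, or 0.005 per factor.
- *F plus sum:* the 5-df joint F test at 5%, with the sum of standardised coefficients below zero.
- *Sum test:* a 1-df test of that sum at two-sided 5%, favourable side only.

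**4. False support with no true association.**
- Holm, independent factors: 1 − 0.995^5 = 2.5%.
- F plus sum: 5% × ½ = 2.5%.
- Sum test: 5% × ½ = 2.5%.
- Best of the three chosen afterwards: at most 3 × 2.5% = 7.5%. Simulated: 5.4% / 5.4% / 5.9% at factor correlation 0 / 0.3 / 0.5.
- For contrast, any one favourable coefficient, unadjusted: 1 − 0.975^5 = 11.9%; simulated 12.1% / 12.1% / 12.6%.

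**5. Power and disagreement when associations exist.** The documents give no effect size or correlation, so these are assumptions: n = 150, 10 model terms, residual SD 1, confounders independent of the factors, one factor binary 50/50, one scored 0 to 2, three continuous, all standardised. The five factors together have partial R² 8%, so f² = 0.08/0.92 = 0.087. There are 10,000 simulated studies per setting. Entries are for correlation 0 / 0.3 / 0.5.

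| | Five equal effects | One factor carries all |
|---|---|---|
| Holm power | 55 / 26 / 17% | 80 / 72 / 57% |
| F plus sum power | 77 / 77 / 77% | 73 / 76 / 76% |
| Sum test power | 93 / 93 / 93% | 34 / 61 / 73% |
| Three rules not unanimous | 41 / 69 / 78% | 53 / 40 / 43% |

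The last row counts any split among three rules. For two analysts the pair matters. F plus sum against the sum test with equal effects must differ in at least 93 − 77 = 16% of studies (simulated 17% to 18%). Holm against the sum test at correlation 0.5 must differ in at least 93 − 17 = 76%.

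**6. What a split means.** All three rules read the same fitted model, so coefficients and intervals are identical. A split is always supported against not shown, never a reversal of direction.

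**7. Is one rule clearly right?** No. The sum test has the most power when effects are equal and much the least when one factor dominates and factors are uncorrelated (34% against 80% for Holm). With mixed signs and a true sum of zero (two factors at −0.20, two at +0.20), F plus sum declares support in 48% / 44% / 39% of studies, the sum test in about 2.5%.

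**The case for a change.** The strongest case for a change is that the protocol commits twice to testing a directional hypothesis, that nothing in it says how, and that a few sentences written before analysis would settle the matter at no cost in data or modelling. Some pairs of reasonable rules disagree in most studies under plausible effects, so the choice is not cosmetic. An analyst who takes any single favourable p-value below 5% as support would also make false claims well above the usual rate.

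Part of this stands. The rule is missing, and the covariate ratio does not supply it. The rest weakens on inspection:

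- The contrast between testing and exploring is mostly wording. Section 3.1 itself also describes the aim as examining a relationship, and Section 7.1 goes on to name outcome, predictors and confounders.
- The large disagreement figures reflect differing power under assumed effects, not false claims.
- The 12% belongs to a rule that the plan does not adopt. A report giving five coefficients with intervals lets any reader apply a stricter threshold.
- The remedy names no single change. It is either a choice among tests with different weaknesses or a relabelling as estimation.

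How the two questions on end-of-life preferences become one predictor is a separate scoring matter and adds no weight here.

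**Conclusion.** No change to the plan follows. Section 7.1 leaves out an alpha and a decision rule, but the analysis it describes is sound and yields five interpretable adjusted coefficients that no choice of rule would alter. What is open is a label, supported or not shown, in a cross-sectional observational study where no treatment or stopping decision depends on it. The planned use of the results, a resource for carers built on the factors most closely tied to grief, rests on the relative size of the coefficients, which Section 3.2 makes an objective of its own.

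The harm from late choice among the three directional rules is small: 5.4% to 5.9% false support against 2.4% to 2.7% for any one of them. That result needs no assumed effect, but it does rest on the assumed scoring and correlations. The power and disagreement figures depend on an assumed block partial R² of 8% and cannot show an error in the plan. This is a detail that analysts can fill sensibly by reporting the five coefficients with 95% confidence intervals and saying how they read them. Which formal rule to prefer is a fair trade-off.

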3.2 Secondary Objectives

- To examine the prevalence and severity of grief before the death in carers of people with dementia (Quantitative interviews)
- To identify which modifiable factors reflecting preparation for end of life are most strongly related to grief before the death (Quantitative interviews)
- To examine the extent to which carers feel prepared for the future and end-of-life care for their relative with dementia (Quantitative and qualitative interviews)
- To explore whether carers recognize grief during caring and what supports they think would be helpful (Quantitative and qualitative interviews)
- To identify unmet needs for information about end of life symptoms and emotional support for carers (Qualitative interviews)
- To explore how carers experience and cope with changes in grief over time (Qualitative interviews)

